9.4 DATA SOURCES

This study will use data from Optum’s Clinical Electronic Health Record (EHR) database. This database aggregates clinical treatment data from a provider network of over 140,000 physicians at more than 600 hospitals and more than 6,500 clinics. The EHR database currently has more than 60 million unique patients across the United States and Puerto Rico. The demographics of patients within the Optum EHR data are representative of the United States population ([Table 3](#)).

The data are provided by more than 46 contributors, including the nation’s leading medical groups, integrated delivery networks (IDNs), and hospital chains. Using deterministic matching technology, Optum collects the provider data from different platforms and IT systems (e.g., Cerner, Epic, GE, McKesson), and then normalizes, validates, and integrates it. The result is a longitudinal record that delivers a comprehensive spectrum of health and medical information. Records in the database are updated quarterly.

Table 3. Optum EHR Data Patient Demographics Compared with the US Population

Attribute	Optum Lives, 2015	US Healthcare Utilizers ¹	US Population ²
Gender			
Male	43%	47%	49%
Female	57%	53%	51%
Age Group			
0-9	10%	13%	13%
10-17	7%	10%	11%
18-24	7%	8%	10%
25-34	12%	13%	14%
35-44	12%	12%	13%
45-54	14%	13%	14%
55-64	15%	14%	13%

¹ Source of US estimate of healthcare utilizers by age & sex: US Department of Health & Human Services, Agency for Healthcare Research & Quality, Medical Expenditure Panel Survey (MEPS), Projected Expenditure Data File for 2015. Percent of US population with non-zero medical expenditures found from MEPS and applied to US population estimate for 2015 from US Census Bureau, Current Population Survey.

² Source of estimate of US population totals alone and by insurance type: US Census Bureau, Current Population Survey, Annual Social and Economic Supplement, 2015.

Attribute	Optum Lives, 2015	US Healthcare Utilizers ¹	US Population ²
65-74	12%	9%	9%
75+	10%	8%	6%
US Region			
Northeast	13%		18%
Midwest	35%		21%
South	38%		37%
West	14%		24%
Race/Ethnicity			
White	62%	66%	62%
African American	9%	11%	12%
Hispanic	6%	16%	18%
Asian	2%	5%	5%
Other/Unknown	21%	3%	3%
Insurance Coverage			
Commercial	66%	61%	58%
Medicare	14%	17%	16%
Medicaid/ Other gov't	12%	13%	15%
Uninsured	8%	9%	10%

9.5 STUDY SIZE

This study is exploratory and not characterized with *a priori* hypotheses. All patients identified in the data that meet the inclusion criteria and do not meet the exclusion criteria will be included in the study population.

A sample size calculation was conducted to determine the minimum number of patients that would be required to detect a change in HbA1c of at least 0.5% among the cohort groups. Based on previously published studies, it was assumed that the standard deviation for the 24-

week mean change in HbA1c from baseline could range between 1.2 (based on the placebo adjusted value in the MARLINA-T2D trial (20)) and 1.5 (based on retrospective studies of diabetes treatments using electronic medical record data from across the United States (21)). Assuming a SD of 1.2 for the change in HbA1c, at least 92 patients would be needed in each of the two smallest groups of the cohort of interest (e.g., age, renal function, age by renal function) in order to have 80% power to detect a mean difference in HbA1c of at least 0.5% using a two-sided test at an alpha of 0.05. If the standard deviation for the change in HbA1c is 1.5, then 143 patients would be needed in each of the two smallest groups.

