- Pre-index renal function—Pre-index renal function will be assessed using estimated glomerular filtration rate (eGFR) which will be calculated using the Chronic Kidney Disease Epidemiology Collaboration (CKD-EPI) equation (18). This equation

requires variables for serum creatinine, age, sex, and race but weight and height are not required because the results are normalized to 1.73 m² body surface area (an accepted average adult surface area) (19). The last (most recent) serum creatinine value in the pre-index period (including the index date) will be used for the serum creatinine (Scr) variable. The CKD-EPI equation (18) to estimate GFR in units of ml/min/1.73m² after incorporating multiplication factors for race and sex into the intercept is displayed in [Table 2](#). For purposes of this eGFR calculation, race will be categorized as either AA or non-AA (includes White, Asian and Other/Unknown).

Table 2. CKD-EPI equation (Adapted from Reference 18)

Race	Sex	Scr (mg/dL)	Equation for eGFR in units of ml/min/1.73m ²
AA	Female	≤ 0.7	$eGFR = 166 \times \left(\frac{Scr}{0.7}\right)^{-0.329} \times (0.993)^{Age}$
AA	Female	> 0.7	$eGFR = 166 \times \left(\frac{Scr}{0.7}\right)^{-1.209} \times (0.993)^{Age}$
AA	Male	≤ 0.9	$eGFR = 163 \times \left(\frac{Scr}{0.9}\right)^{-0.411} \times (0.993)^{Age}$
AA	Male	> 0.9	$eGFR = 163 \times \left(\frac{Scr}{0.9}\right)^{-1.209} \times (0.993)^{Age}$
Non-AA	Female	≤ 0.7	$eGFR = 144 \times \left(\frac{Scr}{0.7}\right)^{-0.329} \times (0.993)^{Age}$
Non-AA	Female	> 0.7	$eGFR = 144 \times \left(\frac{Scr}{0.7}\right)^{-1.209} \times (0.993)^{Age}$
Non-AA	Male	≤ 0.9	$eGFR = 141 \times \left(\frac{Scr}{0.9}\right)^{-0.411} \times (0.993)^{Age}$
Non-AA	Male	>0.9	$GFR = 141 \times \left(\frac{Scr}{0.9}\right)^{-1.209} \times (0.993)^{Age}$

- Pre-index renal function categories—Patients will be categorized into one of the following renal function groups based on their eGFR during the pre-index period (including the index date):
 - < 30 ml/min/1.73m²
 - 30 to 44 ml/min/1.73m²
 - 45 to 59 ml/min/1.73m²
 - 60 to 89 ml/min/1.73m²
 - ≥ 90 ml/min/1.73m²
 - Not available

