9.7 DATA ANALYSIS

9.7.1 Feasibility Assessment

Feasibility analyses will include determinations of the number of patients in each potential category of age and renal function. Some cells may be too small (e.g. eGFR 30 to 44 ml/min/1.73m²), but as long as most of the key groups have sufficient numbers (as described in Section 9.5 Study Size) of patients this will not detract from the overall results. The number of AA individuals will not be as large as the full data set and as such some of the age and eGFR groups will be much smaller than for the whole group. Since the AA subgroup analysis is exploratory, having some small groups will not significantly limit the overall clinical interpretation even if statistical comparability cannot be confirmed.

Optum conducted a feasibility analysis using data from the Optum EHR database. There were 63,499 patients identified with a written prescription for linagliptin between January 1, 2012 and June 30, 2016. After excluding patients without data available for a six-month pre-index period, patients with a prescription for linagliptin or other DPP-4 inhibitor, and patients less than 40 years of age, the patient count was reduced to 38,868 patients.

A total of 16,566 patients had at least one HbA1c result during the six-month period prior to the index date and at least one HbA1c result during the six-month period after the index date. Of these, 16,566 adult patients were newly initiated on linagliptin with baseline and follow-up HbA1c results, race/ethnicity was available in 15,289 patients, a serum creatinine value was available for 15,130 patients, and both race/ethnicity and serum creatinine were available for 13,962 patients.

Among the 13,962 patients meeting the criteria and with a baseline serum creatinine, the smallest age group cell (40-54 years) had more than 2,500 patients and the cell with age > 75 years (which is of special interest in this protocol) had more than 3,000 patients. Thus, for the primary end point to assess HbA1c across age ranges, each category is of sufficient size to conduct this study.

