9.7.2 Primary Analysis

For the primary analysis, study variables, including pre-index and outcome measures, will be analyzed descriptively. Numbers and percentages will be provided for dichotomous and categorical variables. Means, medians, and standard deviations will be provided for continuous variables.

Results will be stratified by age, renal function, and race/ethnicity. Pre-index and outcome measures will be reported for the overall study population as well as stratified by predefined subgroups of patients.

The following stratifications will be conducted among the overall study population:

- By age categories defined as 40 to 54 years, 55 to 64 years, 65 to 74 years, and ≥ 75 years
- By renal function categories (based on eGFR) defined as: < 30 ml/min/1.73m², 30 to 44 ml/min/1.73m², 45 to 59 ml/min/1.73m², 60 to 89 ml/min/1.73 m², ≥ 90 ml/min/1.73m², and not available
- By race defined as White, African American, Asian, or Other/Unknown

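### The one-way age and eGFR tables and the unadjusted tests mix age with renal function, and the planned model that would separate them is optional and covers only one of the two outcomes

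*Combined protocol and SAP*

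**What the plan says.** - **Study size (9.5).** The minimum applies to "each of the two smallest groups of the cohort of interest (e.g., age, renal function, age by renal function"). It is a two-group calculation: "80% power to detect a mean difference in HbA1c of at least 0.5" points, "using a two-sided test at an alpha of 0.05". It gives 92 per group for an SD of 1.2 and 143 for an SD of 1.5.
- **Feasibility (9.7.1).** The plan promises "determinations of the number of patients in each potential category of age and renal function". It reports 13,962 patients with race/ethnicity and creatinine, more than 2,500 aged 40-54 and more than 3,000 over 75. It gives no counts by eGFR or by age and eGFR together.
- **Primary analysis (9.7.2).** "The following stratifications will be conducted among the overall study population": by age, by eGFR category and by race, as three separate lists.
- **Secondary analysis (9.7.3).** Strata are compared with t-tests and chi-square tests. An OLS model for change in HbA1c (MMRM if repeated values are common) is an option that depends on the group sizes in 9.5. Its covariates include age categories, eGFR categories and pre-index HbA1c, with no product term. No model is given for HbA1c <7.0%.
- **Renal function (9.3.3.2).** The CKD-EPI equation "requires variables for serum creatinine, age, sex, and race". All eight rows of Table 2 carry the factor 0.993^Age.

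**The concern.** The primary objective describes change in HbA1c across age and renal categories, and Section 9.1 frames the question as comparable effectiveness across both. Because age enters the eGFR formula, the low-eGFR strata will tend to be older and the high-eGFR strata younger, even if creatinine does not vary with age. A one-way renal table then carries part of any age effect, and a one-way age table carries part of any renal effect. This can produce a gradient that is not there. If the two effects oppose each other, it can also hide a real one, which would look like the comparability the study hopes to show. The limitations in 9.9 discuss baseline HbA1c and diabetes duration as differing between groups, but not this overlap. Section 9.5 also names age-by-renal groups that no analysis in the supplied text uses.

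**Working it through.** **1. The plan's own figure.** Inputs from 9.5: two-sided alpha 0.05, power 80%, difference 0.5, SD 1.2 or 1.5.

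n per group = 2 × (1.96 + 0.8416)² × SD² / 0.5²

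- SD 1.2: 2 × 7.849 × 1.44 / 0.25 = 90.4, so 91. With the t distribution, 91.4, so 92.
- SD 1.5: 2 × 7.849 × 2.25 / 0.25 = 141.3, so 142. With the t distribution, 142.2, so 143.

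The stated 92 and 143 are reproduced.

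**2. What an interaction would need.** A difference of differences across four equal cells has twice the variance: n per cell = 4 × 7.849 × SD² / 0.25 = 180.8 (181) for SD 1.2 and 282.6 (283) for SD 1.5. This is for scale only, since the supplied plan tests no interaction.

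**3. Age inside eGFR.** From Table 2, 0.993^35 = 0.782, so at the same creatinine eGFR is 22% lower at 80 than at 45. Examples with the non-African-American coefficients:

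| Patient | eGFR at 45 | eGFR at 80 |
|---|---|---|
| Man, creatinine 1.0 | 90.5 (≥90) | 70.8 (60-89) |
| Man, creatinine 1.2 | 72.6 (60-89) | 56.8 (45-59) |
| Woman, creatinine 1.2 | 54.7 (45-59) | 42.8 (30-44) |

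A man reaches eGFR ≥90 with creatinine up to about 1.00 at age 45, but only up to about 0.68 at age 80.

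**4. Possible size of the mixing (assumed inputs).** With two age groups, the false renal contrast is the age effect times the difference in age mix. If patients ≥75 differ by 0.2 and make up 50% of one renal group and 10% of another, it is 0.2 × (0.50 − 0.10) = 0.08.

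A simulation gives a range. Assumptions:
- age-group shares of 18/30/30/22% (compare 2,500/13,962 = 17.9% and 3,000/13,962 = 21.5%);
- half men, non-African-American coefficients;
- median creatinine at age 65 of 1.05 (men) and 0.85 (women), SD of log creatinine 0.35;
- log creatinine rising by 0 to 0.01 per year of age;
- no renal effect, and an age effect D spread evenly from the youngest to the oldest group.

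The one-way contrast of eGFR <30 against ≥90 is then:
- D = 0.5: 0.149 (creatinine unrelated to age) to 0.272 (rising 1% per year).
- D = 0.2: the contrast is proportional to D, so 0.4 × 0.149 = 0.06 to 0.4 × 0.272 = 0.11.

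In the same data, an additive model with both factors returns a renal effect of 0.

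**5. Room for a crossed table.** 4 × 5 = 20 cells. Reaching the 9.5 minimum in every cell needs at least 20 × 92 = 1,840 or 20 × 143 = 2,860 patients, against 13,962 (average 698 per cell). Cells will be uneven. Under the same assumptions:
- age 40-54 with eGFR <30: about 5 to 21 patients;
- age ≥75 with eGFR ≥90: 118 to 264;
- age ≥75 with eGFR <30: 105 to 292;
- age ≥75 with eGFR 30-44: 494 to 799.

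**The case against.** The strongest reply is that 9.7.3 already puts age and eGFR categories in one model with pre-index HbA1c. Step 4 confirms that such a model removes the false contrast. Its results tables have a date in Section 6 (2 February 2018), the reported age groups are far above 92 or 143, and if groups prove small the plan collapses categories or uses continuous terms, which keeps both factors in. This stands: for change in HbA1c, the main effects would probably be separated. It does not reach the one-way tables, the unadjusted tests, or goal attainment, and the model remains optional.

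A second reply is that the primary objective is descriptive and the study exploratory, and that 9.9 already warns of baseline differences between categories. One-way means do correctly describe the patients in each category. The difficulty arises when they are read as effects of age or of renal function, which the comparative aim invites.

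Third, the supplied text may be incomplete on this point. Section 9.2.3 cites a Section 9.7.4.4 that does not appear in it, and the table shells sit in a separate analysis plan. A crossed analysis may be specified there.

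Fourth, the 9.5 mention is only an example under a generic calculation, and the cells that 9.7.1 names are one-way, so its wording does not clearly promise crossed counts. Both points are fair.

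**Conclusion.** The point holds for the one-way tables in 9.7.2 and the unadjusted comparisons in 9.7.3. That age shifts the renal category follows from Table 2 and needs no assumption. The amount of distortion does: roughly 0.06 to 0.27 points under the inputs above, against the 0.5 the study was sized to detect, and nothing if HbA1c change does not vary with age. Section 7 expects similar reductions across ages, so the lower end may be nearer.

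A reader might infer more than the documents support:
- **That the study cannot separate age from renal function.** The 9.7.3 model would do so for change in HbA1c.
- **That it cannot describe older patients with low eGFR, the group its rationale is about.** The rationale treats age and low eGFR separately, those cells look usable under the assumptions above, and a crossed analysis may be specified in text not supplied.
- **That 92 and 143 are wrong.** They are correct for a difference between two groups.

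What remains is a gap worth closing because closing it is cheap.

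**What to change.** - **9.7.2:** add a 4 × 5 age-by-eGFR table with n, mean pre-index HbA1c, mean change with 95% CI, and percent below 7.0%. Beside the one-way results, give renal means standardised to the overall age distribution and age means standardised to the overall eGFR distribution. If Section 9.7.4 or the analysis plan already does this, cite it instead.
- **9.7.3:** commit to the mutually adjusted model for change in HbA1c, keeping the existing fallback of collapsed or continuous terms. Add a logistic model with the same covariates for goal attainment. Report one exploratory age-by-eGFR trend interaction. The full categorical interaction, with 3 × 4 = 12 degrees of freedom, is not needed.
- **9.5:** leave 92 and 143 as they are. State whether age by renal function is to be analysed, and that these figures do not size an interaction.

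Cost: no new data, some programming, and a few more exploratory estimates in a study that does not adjust its p-values. Some cells will be thin, most likely young patients with eGFR <30. Their intervals will be wide, and so will any standardised mean that gives them weight. Print the cell counts so that readers can see this.

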9.6 DATA MANAGEMENT

Optum stores all extracted data on secure servers. Data files for patients who meet the inclusion criteria will be extracted from the database using Oracle® and SAS® -based tools and housed on Optum UNIX® servers for programming and analysis by Optum staff.

9.7 DATA ANALYSIS

9.7.1 Feasibility Assessment

Feasibility analyses will include determinations of the number of patients in each potential category of age and renal function. Some cells may be too small (e.g. eGFR 30 to 44 ml/min/1.73m²), but as long as most of the key groups have sufficient numbers (as described in Section 9.5 Study Size) of patients this will not detract from the overall results. The number of AA individuals will not be as large as the full data set and as such some of the age and eGFR groups will be much smaller than for the whole group. Since the AA subgroup analysis is exploratory, having some small groups will not significantly limit the overall clinical interpretation even if statistical comparability cannot be confirmed.

Optum conducted a feasibility analysis using data from the Optum EHR database. There were 63,499 patients identified with a written prescription for linagliptin between January 1, 2012 and June 30, 2016. After excluding patients without data available for a six-month pre-index period, patients with a prescription for linagliptin or other DPP-4 inhibitor, and patients less than 40 years of age, the patient count was reduced to 38,868 patients.

A total of 16,566 patients had at least one HbA1c result during the six-month period prior to the index date and at least one HbA1c result during the six-month period after the index date. Of these, 16,566 adult patients were newly initiated on linagliptin with baseline and follow-up HbA1c results, race/ethnicity was available in 15,289 patients, a serum creatinine value was available for 15,130 patients, and both race/ethnicity and serum creatinine were available for 13,962 patients.

Among the 13,962 patients meeting the criteria and with a baseline serum creatinine, the smallest age group cell (40-54 years) had more than 2,500 patients and the cell with age > 75 years (which is of special interest in this protocol) had more than 3,000 patients. Thus, for the primary end point to assess HbA1c across age ranges, each category is of sufficient size to conduct this study.

9.7.2 Primary Analysis

For the primary analysis, study variables, including pre-index and outcome measures, will be analyzed descriptively. Numbers and percentages will be provided for dichotomous and categorical variables. Means, medians, and standard deviations will be provided for continuous variables.

Results will be stratified by age, renal function, and race/ethnicity. Pre-index and outcome measures will be reported for the overall study population as well as stratified by predefined subgroups of patients.

The following stratifications will be conducted among the overall study population:

- By age categories defined as 40 to 54 years, 55 to 64 years, 65 to 74 years, and ≥ 75 years
- By renal function categories (based on eGFR) defined as: < 30 ml/min/1.73m², 30 to 44 ml/min/1.73m², 45 to 59 ml/min/1.73m², 60 to 89 ml/min/1.73 m², ≥ 90 ml/min/1.73m², and not available
- By race defined as White, African American, Asian, or Other/Unknown

9.7.3 Secondary Analysis

For the secondary analysis, results will be stratified by age, renal function, and race/ethnicity. Comparisons of pre-index characteristics and outcome measures across age, renal function, and race/ethnicity strata will be provided, and appropriate tests will be used based on the distribution of the measure. Continuous measures will be compared using t-tests and categorical measures will be compared using chi-square tests. P-values and 95% confidence intervals will be reported. Reported p-values will not be adjusted for multiple comparisons.

In addition, as part of the secondary analysis, multivariable modelling will be considered to assess change in HbA1c, controlling for an a priori list of covariates. The use of multivariable modelling will be dependent on having robust sample size distribution (as defined in Section 9.5 Study Size) across age and eGFR categories.

Since the primary outcome of change in HbA1c is calculated using just two timepoints, pre-index and follow-up, multivariable analysis will be conducted using ordinary least squares (OLS). In the event that the assumption that the majority of patients have only one HbA1c measure during the follow-up period turns out to be false and there are multiple HbA1c values per patient during this timeframe, mixed models repeated measures (MMRM) will be used to control for the correlation of multiple HbA1c observations from the same patient.

Following standard procedure, regression diagnostics will be performed for each model to assess goodness of fit and violations of model assumptions (e.g., multicollinearity,

heteroskedasticity). When there are violations of the model, Optum will note them and make appropriate corrections to the data (i.e., typically through transformation of either the independent or dependent variables) or in the method of estimation.

The following list of covariates will be included in the model provided sufficient sample size distribution:

- Age categories (40 to 54 years, 55 to 64 years, 65 to 74 years, and ≥ 75 years)
- Sex
- Race
- Ethnicity
- Geographic region
- Pre-index HbA1c
- Pre-index renal function categories based on eGFR (< 30 ml/min/1.73m², 30 to 44 ml/min/1.73m², 45 to 59 ml/min/1.73m², 60 to 89 ml/min/1.73m², and ≥ 90 ml/min/1.73m²)
- Pre-index Quan-Charlson comorbidity score
- Pre-index individual comorbidities (each of the AHRQ top 20 comorbidities identified for this population will be included unless the comorbidity is already included in the Charlson Comorbidity Index)

Age and renal function categories will be assessed for adequate sample size across categories based on the sample size calculation reported in Section 9.5. If the sample size distribution is not sufficient to evaluate age as a categorical variable, age will be included as a continuous variable in the model. The eGFR categories of 45 to 59 ml/min/1.73m² (Stage 3A kidney disease) and 30 to 44 ml/min/1.73m² (Stage 3B kidney disease) will be collapsed into one category (Stage 3 kidney disease) if there is not sufficient sample to evaluate as separate categories.. If the sample size distribution is still not sufficient across the eGFR categories, then eGFR will be included as a continuous variable in the model.

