	
 • By age categories defined as 40 to 54 years, 55 to 64 years, 65 to 74 years, and ≥ 75 years • By renal function categories (based on eGFR) defined as: < 30 ml/min/1.73m², 30 to 44 ml/min/1.73m², 45 to 59 ml/min/1.73m², 60 to 89 ml/min/1.73 m², ≥ 90 ml/min/1.73m², and not available • By race defined as White, African American, Asian, or Other/Unknown 
Secondary analysis
 
Comparisons of pre-index characteristics and outcome measures will be provided, and appropriate tests will be used based on the distribution of the measure. Continuous measures will be compared using t-tests and categorical measures will be compared using chi-square tests. P-values and 95% confidence intervals will be reported. Reported p-values will not be adjusted for multiple comparisons.
 
In addition to the descriptive analyses described above, multivariable modelling will be considered to assess change in HbA1c, controlling for an a priori list of covariates. The use of multivariable modelling will be dependent on having robust sample size distribution across age and eGFR categories.

Milestones:
	
Protocol Completion Data Extraction, Preparation & QA Data Analysis Final Report

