9.9 LIMITATIONS OF THE RESEARCH METHODS

This study has several limitations inherent to its non-interventional study design. There may be baseline differences in the different age and renal function categories. In randomized clinical trials, these differences are mitigated by randomization. Among the important considerations is if there are substantial differences in baseline HbA1c. It is well known that the change from HbA1c is a function of baseline HbA1c, ie, the higher the baseline HbA1c, the greater the change from baseline even with comparable doses of the glucose lowering medication. This observation has been confirmed by Esposito et al (22) in their analyses of several DPP4 inhibitors.

Second, we have selected a follow up window of 6 months rather than a longer window e.g. up to 1 year. Maximal effectiveness is usually achieved by 6 months, although in randomized controlled trials HbA1c values may be lower at later time points. This limitation is balanced against the observation that medication persistence at 6 months will likely be

better than at 12 months and the fact that we wish to maximize the numbers of patients in each of the age and renal function cells.

Third, duration of T2DM is likely to be longer in patients with lower renal function. Increased duration of diabetes is also associated with greater reductions in beta cell function. Since one of the mechanisms of DPP4 inhibitor medications is to increase GLP-1 mediated insulin secretion, reduced renal function could theoretically be associated with diminished glycemic effectiveness. If the current study supports this observation, this will confound the claim of comparable glycemic effectiveness across the range of renal function, but it will be an important observation for the management of T2DM patients. Lajra et al reported on a retrospective analysis of 202 patients from two separate trials in which patients with > 10 years of diabetes were randomized to linagliptin 5 mg (n = 122) or placebo (n = 80)(15). The placebo adjusted mean difference in HbA1c was -0.66% (95% CI -0.85 to -0.38). No direct comparisons were made with shorter duration of diabetes. However, these data suggest that differences in duration of diabetes are unlikely to have a major effect on the data obtained in the current proposal.

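### For secondary objective 1 the plan commits without condition only to unadjusted t-tests, leaves the baseline-adjusted regression conditional, and does not say which estimate answers the objective

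*Combined protocol and SAP*

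**What the plan says.** The first secondary objective (Section 8) is to compare change in HbA1c across the age and renal function categories.

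**Stated without condition.** Section 9.7.3 says that strata will be compared with tests suited to the distribution of the measure: "Continuous measures will be compared using t-tests and categorical measures will be compared using chi-square tests". These tests have no covariates. The text does not say how a t-test is to be used with four or five groups.

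**Stated with conditions.** The same section says that "multivariable modelling will be considered to assess change in HbA1c, controlling for an a priori list of covariates", and that "The use of multivariable modelling will be dependent on having robust sample size distribution", with Section 9.5 as the size standard. The covariate list, which includes pre-index HbA1c, is again made subject to sample size. The abstract (Section 4, Data analysis) repeats the condition: "The use of multivariable modelling will be dependent on having robust sample size distribution across age and eGFR categories".

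**Text that treats the model as settled.** Elsewhere 9.7.3 says "multivariable analysis will be conducted using ordinary least squares (OLS"), with a switch to MMRM if patients have multiple follow-up values. Its last paragraph deals with small cells by recoding: age becomes continuous; the two stage 3 eGFR categories are merged; and if that is not enough, "then eGFR will be included as a continuous variable in the model". Section 6 gives a date for the multivariable tables, with no condition attached.

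**What the plan says about baseline.** Section 9.9 says "There may be baseline differences in the different age and renal function categories" and "It is well known that the change from HbA1c is a function of baseline HbA1c".

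**The concern.** The protocol identifies a source of distortion in 9.9, and the only comparison it states without condition leaves that distortion in. If one category starts with a higher HbA1c, a t-test on change can show a difference that is only baseline imbalance, or can hide a real difference when the imbalance works the other way. The stratum tables will show the imbalance but will not remove it from the difference or its p-value.

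This matters because Section 9.1 says the data will be used to determine whether effectiveness is comparable across age and renal function. If the t-test and the regression disagree, the supplied text gives no basis for choosing between them, and the choice would be made after both results are known.

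**Working it through.** **1. The plan's own figures.** Section 9.5 uses a difference of 0.5, 80% power, two-sided alpha 0.05 and SD 1.2 or 1.5. The two-sample t-test calculation gives 91.4 and 142.2 per group, which round up to the stated 92 and 143. The normal approximation, 2 × (1.96 + 0.84)² × SD² / 0.5², gives 91 and 142. The figures reproduce, and they describe an unadjusted two-group comparison.

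**2. Number of comparisons.** Four age categories give 4 × 3 / 2 = 6 pairs. Five eGFR categories give 5 × 4 / 2 = 10.

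**3. Spurious difference.** The documents give neither the slope of change on baseline nor the baseline gap between categories. Assumed: no true difference at equal baseline, a slope of 0.3 to 0.7 points of change per point of baseline, and a gap of 0.1 to 0.5 points.

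Bias = slope × gap, from 0.3 × 0.1 = 0.03 to 0.7 × 0.5 = 0.35.

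**4. False-positive rate of the t-test.** SE = SD × √(1/n₁ + 1/n₂). Rejection rate = P(Z > 1.96 − bias/SE) + P(Z < −1.96 − bias/SE). SD is 1.5. The sizes 2,500 and 3,000 are the lower bounds given in Section 9.7.1 for the smallest and the oldest age cell; final counts may differ.

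| Sizes | SE | Gap 0.1 | Gap 0.2 | Gap 0.5 |
|---|---|---|---|---|
| 2,500 vs 3,000 | 0.0406 | 11 to 41% | 32 to 93% | 96% or more |
| 143 vs 143 | 0.1774 | 5 to 7% | 6 to 12% | 14 to 51% |

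At a gap of 0.2 the bias is 0.06 to 0.14. In the large cells a bias of 1.96 × 0.0406 = 0.08 points gives about a 50% chance of p < 0.05. That is 16% of the 0.5-point planning difference, so a significant result there can be small.

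**5. Masking.** With 143 per group and a true difference of 0.5, an opposing bias of 0.03, 0.15 or 0.35 lowers power from 0.805 to 0.755, 0.505 or 0.135. The last value is the extreme corner of the assumed range.

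**6. Does adjustment remove it?** A simulation used the same null, an assumed baseline SD of 1.5 and 2,000 runs per setting. The settings were 2,500 vs 3,000 with gap 0.2, and 143 per group with gap 0.5, each at slopes 0.3 and 0.7. The regression with pre-index HbA1c rejected in 5 to 6% of runs in all four.

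**7. The other null.** Suppose instead that mean change is equal and each group regresses to its own mean. With 2,500 vs 3,000 and gap 0.2, the t-test rejects in 5 to 6% of runs, while the adjusted model rejects in about 35% (slope 0.3) and nearly 100% (slope 0.7). The two analyses therefore answer different questions.

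**8. Patients without creatinine.** The feasibility counts in 9.7.1 give 16,566 − 15,130 = 1,436 patients, and 1,436 / 16,566 = 8.7%. The eGFR term listed for the model has five levels and no level for unavailable values, although 9.3.3.2 and 9.7.2 define one. A complete-case fit would drop these patients from the age comparison too. This is an inference; no section says how they are handled.

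**The case against.** The strongest reply is that the regression was plainly meant to run. The OLS sentence, the recoding rules and the milestone all say so, and a specific rule for small cells should outrank a general caution. This largely stands. A reader might infer that the plan intends to rely on t-tests alone; the documents do not support that. What remains is that 9.7.3 and the abstract still contain the condition, and that even a model certain to run is not ranked above the t-tests.

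A reader might also infer that one small eGFR cell, such as 30 to 44, could remove the adjusted age comparison. The documents do not support this either. That cell is one of the two that 9.7.3 would merge, and 9.7.1 accepts some small cells as long as most key groups are large enough.

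The high error rates arise in the age cells, which far exceed 92 or 143. There the t-test would probably appear beside an adjusted estimate. The rates also depend on the assumed null (step 7). Section 9.9 leans towards that null but does not establish it across non-randomised groups. Both points stand and limit the weight of the figures.

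Finally, Section 9.5 describes the study as exploratory, 9.9 discloses the dependence on baseline, and no decision rule depends on these p-values. Section 12 and Annex 1, Appendix C refer to an analysis plan for table shells that is not in the supplied text and may already name the estimate.

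**Conclusion.** The point holds as an inconsistency with a missing designation. In 9.7.3 and the abstract the regression is conditional; in the OLS sentence, the recoding rules and Section 6 it is settled; the unadjusted t-tests carry no condition and no multi-group rule; and no supplied section says which estimate answers secondary objective 1. Because 9.9 accepts that change depends on baseline, the choice can alter the conclusion.

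The size is illustrative. At a 0.2-point gap the false-positive rate is 32 to 93% in cells of 2,500 and 3,000, but 6 to 12% at 143 per group. This assumes equal response at equal baseline, a slope of 0.3 to 0.7 and SD 1.5. It does not mean that the study's findings will generally be false, or that the design is invalid. Severity is minor to moderate.

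**What to change.** In 9.7.3 and the abstract:

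1. Remove the tentative and conditional wording. State that the planned regression of change in HbA1c, including pre-index HbA1c (OLS, or MMRM under the existing switch rule), will be run and is the main analysis for secondary objective 1. Let cell size decide only how age and eGFR are coded, as the last paragraph of 9.7.3 already provides.
2. Report an overall test for age and one for eGFR, with adjusted differences and 95% CIs against a stated reference category, or the slope with its 95% CI if the term is continuous.
3. Label the unadjusted t-tests descriptive.
4. Also report the age model without the eGFR term, so that patients without creatinine stay in the age comparison.

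Models adjusted only for pre-index HbA1c may be added as supportive analyses. They need not replace the full model; an eGFR comparison without age would be a debatable main analysis, since the CKD-EPI equation itself contains age. If the separate analysis plan already names the estimate, 9.7.3 should be made to match it.

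The cost is a few sentences and a little extra analysis, with no new data. Two limits should be stated. Residual confounding remains, for example by diabetes duration, which 9.9 expects to be longer at lower renal function. And the adjusted estimate addresses equal response at equal baseline, which is not the same as equal mean change in non-randomised groups.
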